4.3 Exclusion criteria

A subject who meets ANY of the following criteria will be excluded from participation:

High a priori probability of malignancy:

- FNAC Bethesda category V or VI (§15.3, p91) during local reading or central review (§8.2.1, p46);
- Prior radiation exposure / radiotherapy to the thyroid;
- Prior neck surgery or radiation that in the opinion of the PI has disrupted tissue architecture of the thyroid;
- New **unexplained** hoarseness, change of voice, stridor or paralysis of a vocal cord;
 - In case a benign reason has been found (e.g. vocal cord oedema), the patient is eligible;
- Initial diagnosis of the thyroid nodule through the coincidental discovery of a FDG-avid thyroid incidentaloma on PET-scan;
- New cervical lymphadenopathy highly suspicious for malignancy;
 - o In case malignancy is excluded, patient is eligible;
- Previous treatment for thyroid carcinoma or current diagnosis of any other malignancy that is known to metastasize to the thyroid [49];
- Known metastases of thyroid carcinoma;
- Known genetic predisposition for thyroid carcinoma:
 - Familiar Non-Medullary Thyroid Cancer (NMTC)
 - Familiar Papillary Thyroid Cancer (FPTC), assumed if ≥2 primary or 1 primary and ≥3 secondary criteria are met:
 - Primary criteria:
 - PTC in 2 or more 1st degree relatives
 - Multinodular hyperplasia in 3 or more 1st or 2nd degree relatives
 - Secondary criteria:
 - Age <33 year;
 - Multifocal or bilateral tumour
 - T4-tumours
 - Metastases (N1, M1).
 - Familiar Adenomatoid Polyposis Coli syndrome (FAP, Gardner syndrome, APC-gene mutations on chromosome 5q21)

- Morbus Cowden (PTEN mutation on chromosome 10q23.3)
- PTC / nodular thyroid hyperplasia / papillary renal tumours (linked to locus 1q21).

Proven benign disease or insufficient material for a cytological diagnosis:

FNAC Bethesda category I or II (§15.3, p91) during local reading or central review (§8.2.1, p46)

Performance of additional diagnostic test(s) prior to inclusion (or during the course of the trial), (potentially) affecting patient management:

 Any additional diagnostic test performed prior to inclusion, provided that this test is not yet part of routine clinical care (e.g. molecular testing or mutation analysis of cytological material) and that its results might affect patient management or the patient's/referring physician's willingness to participate in the study (§8.2.1, p46).

Inability to undergo randomization:

• Any patient that will receive thyroid surgery for other reasons (e.g. mechanical or cosmetic complaints).

Inability to undergo treatment:

• Inability to undergo surgery in the opinion of the surgeon / anaesthetist.

Contra-indications for FDG-PET/CT:

- Patient has evidence of infection localised to the neck in the 14 days prior to the FDG-PET/CT scan;
- Inability to tolerate lying supine for the duration of an FDG-PET/CT exam (~10-15min);
- Poorly regulated diabetes mellitus (see next item);
- Hyperglycaemia at time of FDG injection prior to PET/CT (fasting serum glucose >200mg/dL [>11.1 mmol/L]);
 - \circ The use of short-acting insulines within 4 hours of the PET scan is not allowed
- If female and fertile: signs and symptoms of pregnancy or a positive pregnancy test / breast-feeding; A formal negative pregnancy test is not obligatory
- (severe) claustrophobia. Low dose benzodiazepines are allowed

General contra-indications:

- Inability to give informed consent;
- Severe psychiatric disorder;

4.4 Sample size calculation

Based on the main objective, it is expected that FDG-PET/CT can reduce unjust treatment from ~73.1% (=136/186 benign lesions >10mm) to ~40.3% (=75/186 false-positive and false-negative lesions >10mm, §1.3, p19). Using G*Power version 3.1.9.2. (and validated using JMP from SAS version 9.0.1, STATA version 12.0SE and PASS version 2011), we computed using an α error probability of 0.025 (=0.05/2, Bonferroni correction for interim analysis) a power of 0.80 and an allocation ratio of N_A:N_B=2:1, we need to include at least 90 patients in total (one-tailed test) to establish this difference (60+30 patients in arm A and B respectively).

Since around 82.7% (=186/225, §1.3, p19) fulfil the size criterion, at least 111 patients (74+37 patients in arm A and B respectively) need to be included. Accounting for additional 15% data loss at the final end-point, 132 patients should be included (88+44 patients in arm A and B respectively) (Figure 2, p40).

This total number of patients could at best (assuming no data loss) discern a reduction of 26.6% unjust treatment in the whole population with an actual α error probability of 0.016 and a power of 0.80. This is based on a reduction from 74.2% (prevalence of benign disease in all 225 patients) to 47.6%. In the experimental arm (88 patients), where the number of false-negative PET is estimated to be ~1.3% (3/225), this number of patients should establish a false-negative rate of maximal 7.5% (actual α error probability of 0.0066 and a power of 0.80). All analyses will be performed according to the intention-to-treat principle, meaning that analysis is based on the initial study-arm allocation and not on the treatment eventually received (e.g. a FDG-PET/CT negative patient in the experimental arm does not refrain from surgery and therefore actually is treated according to the control study arm).

[figure not shown]

Figure 2: Relation between study size (N), study-arm size sizes (n₁ and n₂) and effect size. Empirical relation: N=16.33935*ES^{-1.86986}, R²=.999443). Expected ES=73.1%-40.3%=32.8%

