5.1 Investigational product/treatment

An FDG-PET/CT is a widely available, routinely used diagnostic modality. As elaborated further in §8.3.1, p48, it requires limited preparation, administration of FDG does not result in any adverse events and the risks resulting from the radiation dose (~5 mSv for a whole-body investigation, 3.3-3.5 mSv for an average weighted adult head/neck FDG-PET/LDCT) are limited (see §15.6: Appendix VI: Radiation Ethics Form, p97). All involved centres have their own PET-CT/scanner.

All patients were scheduled for diagnostic thyroid surgery by an experienced surgeon prior to inclusion to this trial. In case of either a positive FDG-PET/CT in the experimental arm or inclusion in the control arm, scheduled surgery will be performed. In case of a negative FDG-PET/CT in the experimental arm, surgery will be cancelled and follow-up will be performed.

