8.4.1 Specific criteria for withdrawal (at the end of the study)

The false-negative FDG-PET/CT ratio is expected to be around 1.3%, but we accept a falsenegative ratio of up to 5% (i.e. the a priori risk of malignancy in any thyroid nodule). After

EFFECTS

inclusion and surgery of all 44 patients in the control study-arm, final analysis will be performed. In case 6 or more of all these 44 patients (π_1 *=13.6%) in the control study-arm have a false-negative FDG-PET/CT, the treating physicians of all PET-negative patients from the experimental study arm will be advised to proceed to diagnostic (hemi)thyroidectomy. This number is based on the cumulative binomial distribution, by solving:

$$\sum_{n=X}^{n=N} \binom{N}{X} \cdot p^X \cdot (1-p)^{N-X} \le \alpha$$

With N=44, p=0.05 and α =0.025 (Bonferroni-adjusted), resulting in X≥6. Single-sided testing was used. Figure 7, p57.

[figure not shown]

Figure 7: Cumulative Binomial Distribution for a sample size of 22 (interim-analysis) or 44 (end-of-study evaluation) for an individual patient probability of a false-negative FDG-PET/CT of 0.05. In case that more than 4/22 patients (18.2%) at time of the interim analysis or 6/44 (13.6%) patients at time of the end-of-study evaluation have a false-positive FDG-PET/CT (in the control study arm), the false-negative probability is larger than the maximum accepted value of 0.05.

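### Section 4.4 presents 7.5% as a maximum false-negative rate that 88 experimental-arm patients will establish, but its figures belong to a test for an excess over 1.33% and assume complete verification

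*Protocol*

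**What the plan says.** After deriving the total of 132 patients from the primary endpoint, section 4.4 adds two statements about what that number can do. The second is about missed cancers. It begins "In the experimental arm (88 patients), where the number of false-negative PET is estimated to be ~1.3% (3/225") and concludes that "this number of patients should establish a false-negative rate of maximal 7.5% (actual α error probability of 0.0066 and a power of 0.80"). The working alpha of the section is one-sided, with an "α error probability of 0.025 (=0.05/2, Bonferroni correction for interim analysis) a power of 0.80".

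Other sections describe how false negatives would be found. Under section 5.1, for a PET-negative patient in the experimental arm, "surgery will be cancelled and follow-up will be performed". Table 2 schedules surgery and histopathology in arm A for PET-positive patients only. Section 3 expects about 32 of the 132 patients to have surgery cancelled, and accepts 12-month follow-up with ultrasound (and FNAC) as the reference standard for them. Section 8.8 says one year may be too short to settle a false-negative fraction and would probably underestimate it. Section 11.4 names the control arm as the one in which both the scan and final histology are obtained. The safety triggers in sections 8.4.1 and 8.7 use that arm.

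**The concern.** Read plainly, the sentence promises an upper bound: the trial will show that no more than 7.5% of patients have a cancer missed by PET. Delayed treatment after a false-negative scan is one of the main individual risks that section 11.4 lists. An ethics reviewer or later reader could therefore take 7.5% as a safety guarantee built into the design.

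Two things undermine that. The quoted alpha and power appear to belong to a test in the opposite direction, one that detects a rate above the expected 1.3%. And the count is placed in the arm where most PET-negative patients will not have histology, so false negatives there are only partly observable within the study period.

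**Working it through.** **Inputs.** n = 88 (section 4.4, all enrolled, no loss). Expected rate p0 = 3/225 = 0.01333 (section 4.4; pooled table in Appendix IV, 3 false negatives among 225). Rate of interest p1 = 0.075, stated alpha 0.0066 and power 0.80 (section 4.4). Working level one-sided 0.025 (section 4.4). X is the number of false negatives, binomial.

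**Step 1: reproduce the stated pair.** Test H0: p = 0.01333 against p > 0.01333.
- Reject at X ≥ 4: P(X ≥ 4 | 88, 0.01333) = 0.0305, above 0.025, so this cut-off is not allowed.
- Reject at X ≥ 5: P(X ≥ 5 | 88, 0.01333) = 0.00662, which matches the stated 0.0066.
- Power: P(X ≥ 5 | 88, 0.075) = 0.798, which matches the stated 0.80.

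So 7.5% is the alternative that this test detects with 80% power.

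**Step 2: what this test leaves open.** Not rejecting means X ≤ 4. P(X ≤ 4 | 88, 0.075) = 0.20 and P(X ≤ 4 | 88, 0.05) = 0.55. As an illustration (the protocol states no such rule), 4 in 88 would be non-significant, while its exact one-sided 97.5% upper limit is 11.2%.

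**Step 3: the test that would support a maximum.** Test H0: p ≥ 0.075 and claim success if X ≤ c.

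| c | alpha = P(X ≤ c given 0.075) | power = P(X ≤ c given 0.01333) | 97.5% upper limit for c/88 |
|---|---|---|---|
| 1 | 0.0085 | 0.67 | 6.2% |
| 2 | 0.035 | 0.89 | 8.0% |

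At one-sided 0.025 only c ≤ 1 qualifies, so power is 0.67. Neither row gives the stated pair of 0.0066 and 0.80.

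**Step 4: incomplete ascertainment.** Steps 1 to 3 take every false negative among the 88 as observed. If only a fraction f is found, the observable rate is f × 7.5%. The protocol gives no f, so these values are assumptions:
- f = 0.8: P(X ≥ 5 | 88, 0.060) = 0.61
- f = 0.5: P(X ≥ 5 | 88, 0.0375) = 0.23

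The 80% power therefore also depends on full verification, which the arm does not plan. The direction is unfavourable for a bound as well: undercounting makes X ≤ 1 easier to reach for the wrong reason.

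**Step 5: precision where histology is planned for everyone.** Exact (Clopper-Pearson) one-sided 97.5% upper limits in the control arm:

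| False negatives | Upper limit, n = 44 |
|---|---|
| 0 | 1 − 0.025^(1/44) = 8.0% |
| 1 | 12.0% |
| 2 | 15.5% |
| 3 | 18.7% |

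These assume no loss. With the protocol's 15% allowance, 44 × 0.85 ≈ 37, and 0 in 37 gives 1 − 0.025^(1/37) = 9.5%.

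**The case against.** The best defence is that the sentence is a loosely worded statement of detectable difference. Section 4.4 uses the verb establish earlier in the sense of detect, and the sentence just before is of that type, giving the smallest reduction the full sample could discern, with its own actual alpha and 0.80 power. On that reading the hypotheses are not reversed and only the phrasing is poor. Part of this stands: alpha, power and n agree, and there is no arithmetic error. It does not rescue the sentence. The words describe a maximum, and even as a detectable difference the 0.80 power needs all 88 patients verified.

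A second defence is that verification is not absent. Some PET-negative patients may choose surgery, or be operated on after the 12-month ultrasound. SO1c plans 12-month and 5-year estimates, and section 8.8 openly discusses underestimation. All true: the limitation is that histology is not planned for these patients, not that none will have it. Section 4.4 does not carry the caveat.

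Third, the sentence drives neither the sample size nor any stopping rule. That limits the consequence to how the trial's safety precision is described.

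A reader might also infer that the 5% criterion fails for the same reason. The documents do not support that. Section 8.4.1 says "we accept a falsenegative ratio of up to 5"% and sets a trigger for evidence of an excess over that figure; it does not claim to exclude 5%.

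**Conclusion.** The sentence is wrong as written. Its figures describe a test for an excess over 1.33% with 80% power at 7.5%, and that does not establish a maximum of 7.5%. For the claim actually made, at the protocol's one-sided 0.025, power is 0.67 rather than 0.80, given n = 88, a true rate of 3/225 and complete ascertainment. The last assumption conflicts with the protocol's own follow-up plan for PET-negative patients in that arm, so 0.80 is not secured under either reading.

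It would go too far to infer that 7.5% could never be excluded. With full verification, 0 or 1 false negatives in 88 would exclude it at 0.025, and 2 would do so at one-sided 0.05 (alpha 0.035, power 0.89). In the control arm, even 0 in 44 leaves 8.0% at the 97.5% level; that statement is specific to this level and assumes no loss. The sample size, the safety triggers and the primary analysis are unaffected.

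**What to change.** Delete the claim of a maximum of 7.5% from section 4.4 and replace it with one of two statements:

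- a detectable alternative: 88 patients give about 80% power to detect a rate of 7.5% against 1.33%, on condition that every patient's disease status is verified; or
- the precision of the histologically verified control arm: exact one-sided 97.5% upper limits of 8.0%, 12.0%, 15.5% and 18.7% for 0, 1, 2 and 3 false negatives in 44, and 9.5% for 0 in 37 after 15% loss.

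In the report, give the control-arm false-negative rate with its exact interval (Table 5 already names Clopper-Pearson) as the verified estimate. Keep the 12-month and 5-year estimates of SO1c, which address how many patients with malignancy are observed without surgery, and label them as likely biased low. Control-arm estimation should sit beside them, not replace them.

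The cost is a less favourable stated precision. No extra patients or procedures are needed, and because only the wording changes, completed recruitment is no obstacle.

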4.5 Feasibility

We expect to include 57 patients per year in all 9 centres (Appendix II: Signed Document of Cooperating Centres, §15.2, p90). This number is based on approximately 160-200 eligible patients per year in these centres (Table 3, p41) and a very conservative inclusion ratio of only 33% (also accounting for patients excluded based on secondary central review of cytology). Based on PALGA-data, around 750-1,000 patients per year are being confronted with a FNAC-indeterminate thyroid nodule, with these 9 centres we roughly expect to cover ~20% of all FNAC-indeterminate patients in the Netherlands.

As we target at a sample size of 132 patients, starting the inclusion of the first patients in June 2015, entering patients in the trial would take approximately 2.5 years (last patient included November 2017). As the patient follow-up is determined to be 12 months, the last data should then be collected November 2018. There are then 6 months remaining for unscheduled procrastination, data-analysis and reporting. Long-term follow-up will be performed no sooner than begin 2023.

With respect to randomization, based on clinical experience, we believe that patients would prefer not to undergo unbeneficial surgery as there is sufficient evidence that limited retardment of definite surgery in malignant disease has little clinical consequences. Therefore we used an allocation ratio of 2:1 of the experimental versus the control arm.

Addendum (20-02-2019):

Currently, we have included all 132 patients in all 15 centres. The final patient was included in November 2018. Patient recruitment and inclusion is now completed. In addition to the estimated number of eligible patients, Table 3 also shows the final number of included patients per centre. We discussed this observed one-year delay in patient inclusion with KWF, who generously granted us a budget-neutral prolongation of the trial until 01-11-2021. As the patient follow-up is determined to be 12 months, the last data should be collected in November 2019. This leaves two years for data analysis and manuscript preparations. Long-term follow-up will be performed no sooner than 2024.

Centre:	Est. eligible patients/yr:	Included nr. Patients:
Amsterdam MC, Amsterdam	~20-30	11
Erasmus MC, Rotterdam	~24	7
Leiden University MC, Leiden	~15-25	19
Maastricht University MC, Maastricht	~15	2
RadboudUMC, Nijmegen	~20-25	13
University MC Groningen, Groningen	~20-25	14
University MC Utrecht Utrecht	~12-24	5
Vrije Universiteit MC, Amsterdam	~13-19	23
Meander MC, Amersfoort	~25	18
HagaZiekenhuis, Den Haag	~10-15	4
OLVG Lucas Andreas	~10-15	6
Rijnstate, Arnhem	~10-15	2
St. Antonius, Nieuwegein	~10-15	3
Isala, Zwolle	~10	5
Reinier de Graaf Gasthuis, Delft	~10	0
TOTAL:	~254	132

 Table 3: Estimated eligible patients and finally included number of patients per participating centre(Appendix II: Signed Document of Cooperating Centres, §15.2, p90).

5. TREATMENT OF SUBJECTS

This study is not an observational study as the (invasive) diagnostic route is dependent on an extra test performed (i.e. FDG-PET/CT).

5.1 Investigational product/treatment

An FDG-PET/CT is a widely available, routinely used diagnostic modality. As elaborated further in §8.3.1, p48, it requires limited preparation, administration of FDG does not result in any adverse events and the risks resulting from the radiation dose (~5 mSv for a whole-body investigation, 3.3-3.5 mSv for an average weighted adult head/neck FDG-PET/LDCT) are limited (see §15.6: Appendix VI: Radiation Ethics Form, p97). All involved centres have their own PET-CT/scanner.

All patients were scheduled for diagnostic thyroid surgery by an experienced surgeon prior to inclusion to this trial. In case of either a positive FDG-PET/CT in the experimental arm or inclusion in the control arm, scheduled surgery will be performed. In case of a negative FDG-PET/CT in the experimental arm, surgery will be cancelled and follow-up will be performed.

5.2 Use of co-intervention

As elaborated further, co-interventions include questionnaires (§8.3.3) and confirmatory ultrasounds of the neck after 12 months in a subset of patients (§8.3.2).

5.3 Escape medication

Not applicable.

6. INVESTIGATIONAL PRODUCT

6.1 Name and description of investigational product(s)

FDG-PET/CT is a routinely used diagnostic modality. It is used for many oncological and nononcological purposes, including DTC. We do not investigate a new or non-authorised form. Therefore we do not consider FDG-PET/CT an 'investigational product'.

6.2 Summary of findings from non-clinical studies

Not applicable.

6.3 Summary of findings from clinical studies

See §1.3, p19 and our published meta-analysis [4].

6.4 Summary of known and potential risks and benefits

See chapter 13, p78 for a structured risk analysis including all study details.

6.5 Description and justification of route of administration and dosage

Not applicable.

6.6 Dosages, dosage modifications and method of administration

FDG-doses will be given according to the EANM guidelines and are dependent on (age), bodyweight, PET-scanner sensitivity (including 2D/3D acquisition) and scan-speed (minutes per bed position, overlap-percentage), §8.3.1, p48 [50]. Every institution can use its own optimised dosing and acquisition protocol.

6.7 Preparation and labelling of Investigational Medicinal Product

FDG is commercially available throughout multiple vendors in the Netherlands (e.g. BV Cyclotron, VU, Amsterdam; IBA-molecular; GE Healthcare).

6.8 Drug accountability

Not applicable.

7. NON-INVESTIGATIONAL PRODUCT

No non-investigational medicinal product is used in the study: no challenge agents nor products used to assess end-points in the trial are used. No medicinal product such as food products or a chemical compounds or stable isotopes or other products are used.

7.1 Name and description of non-investigational product(s)

Not applicable.

7.2 Summary of findings from non-clinical studies

Not applicable.

7.3 Summary of findings from clinical studies

Not applicable.

7.4 Summary of known and potential risks and benefits

Not applicable.

7.5 Description and justification of route of administration and dosage Not applicable.

7.6 Dosages, dosage modifications and method of administration Not applicable.

7.7 Preparation and labelling of Non Investigational Medicinal Product Not applicable.

7.8 Drug accountability

Not applicable.

8. METHODS

8.1 Study parameters/endpoints

8.1.1 Main study parameter/endpoint

The fraction of unbeneficial treatment (i.e. surgery in benign disease plus watchful waiting in malignant disease) in both study arms based on intention-to-treat.

8.1.2 Secondary study parameters/endpoints

Secondary treatment outcome parameters (SO1, §2.2.1, p30):

- Complication fraction
 - Complications include: bleeding (requiring intervention or prolonging admission), infection (requiring intervention or prolonging admission), re-operation, ICUadmission, (temporary) hoarseness, (temporary) thyroid hormone suppletion or calcium/vitamin D suppletion.
- FDG-PET/CT diagnostic accuracy,
 - True-positive
 - True-negative
 - o False-positive
 - o False-negative
- Fraction of extra diagnostics due to coincidental FDG-PET/CT-findings,
- (Overall Survival and Disease Free Survival determined when last study-related followup of last included patient has been completed),
- Description of factors hampering implementation,
- As this study is performed intention-to-treat: the fraction and reasons of patients in the experimental study arm that still want a hemithyroidectomy despite a negative FDG-PET/CT scan.

Secondary HRQoL outcome parameters (SO2, §2.2.2, p30):

- Personal assessment in all domains of the EQ-5D-5L, the RAND-36 v2.0 (validated translation of the SF36-II), the ThyPRO and the Distress Thermometer (without the problem list) (including temporal relation),
- From the utility (EQ-5D-5L index) and overall survival, the number of QALYs are determined.

Secondary costs and cost-effectiveness parameters (SO3, §2.2.3, p31):

- Volumes of care including hospitalization days,
- iNMB (using QALYs saved as effect) including sensitivity analysis,
- iNMB (using unbeneficial treatment prevented as effect),
- Results of the iPCQ and iMCQ domains, including sick leave days.

Secondary tissue (nodule) parameters (SO4, §2.2.4, p31):

Performed on all (benign and malignant) resected lesions:

- US features (size, border, halo, calcifications, etc.)
- FDG-PET/CT features (SUV_{max}, SUV_{peak}, SUV_{mean}, metabolic volume, TLG)
- Cytological morphological features (Bethesda criteria, atypia, etc.)
- Histological morphological features (diagnosis, invasiveness, stage, atypia, etc.)
- Cytological and histological immunohistochemical features ((semi)quantitative: e.g. GLUT, HK, CA-IX, HIF-1α, Ki67/MIB, caspase-3, galectin-3, Tg, CD3, CD31/34)
- Cytological (tumour)genetic features and biomarkers: genetic profiling for gene alterations (mutations, fusions, rearrangements), gene expression, miRNA expression, and copy-number variations using next-generation sequencing and/or multigene classifier.

